11.6.1. Primary Endpoints

11.6.1.1. Safety Endpoints

Adverse events

All adverse events will be classified by MedDRA, version 19 or higher.

A treatment-emergent adverse event (TEAE) is defined as an AE with start date/time on or after the first administration of investigational medicinal product (IMP). A pre-treatment AE is defined as an AE with start date/time prior to the first administration of IMP.

The following summary tables will be created, reporting number of events and number of patients with events by MedDRA System Organ Class and Preferred Term for the TEAEs:

- total TEAEs
- total serious TEAEs
- total IMP related serious TEAEs
- TEAEs leading to GM-CSF/TG02 withdrawal
- TEAEs leading to study withdrawal
- TEAEs leading to death
- TEAEs by severity
- Related TEAEs by severity
- TEAEs by relationship to each IMP (related, not related) separately

Safety laboratory data

Numerical laboratory data, separately for each parameter, will be summarized in terms of descriptive statistics, as described in [section 11.4](#), by time point of measurement, for absolute value, absolute and relative change from baseline. Further, number of patients with abnormal and/or clinical significant values will be presented by time point.

Vital signs

Blood pressure, heart rate and body temperature will be summarized in terms of descriptive statistics, as described in [section 11.4](#), by time point of measurement, for absolute value, absolute and relative change from baseline.

ECG

Number of patients with abnormal findings in ECG evaluation will be reported by time point of measurement.

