3.4 Sample Size

The study will include up to 16 patients; approximately 4-6 patients in Part I and up to 10 patients in Part II if sponsor decision to initiate such. As this is an exploratory study, no formal samples size calculation has been performed. However, it is estimated that a sample size of 6 patients in each group (monotherapy and combined treatment) is sufficient to explore the potential effect of TG02 to induce immune responses and to assess safety in the induction phase.

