5.2 Adverse Events

Any events that are unequivocally due to progression of disease will not be reported as AEs or SAEs.

Adverse events will be coded according to the latest MedDRA dictionary version.

A treatment-emergent adverse event (TEAE) is defined as an AE with start date/time on or after the first administration of IMP. A pre-treatment AE is defined as an AE with start date/time prior to the first administration of IMP.

There will be no imputation of unknown dates for the calculation of duration or study day. However, for sorting and assignment, if the start date is unknown then it will be assumed to be treatment emergent unless the partial start date or other data (i.e. stop date) indicates differently.

Assessment of AE severity will be based on the NCI CTCAE which includes five grades, with grade 5 being death. If the severity of an event changes during the course of that event, only the maximum severity/grade will be summarised in the tables.

The relationship to each IMP (TG02, GM-CSF, pembrolizumab) is assessed as not related or related.

An overview summary table will summarise the number of events and the number and percentage of patients with at least one of the following TEAEs:

- total TEAEs
- total serious TEAEs
- total IMP related serious TEAEs
- TEAEs leading to TG02 and GM-CSF withdrawal
- TEAEs leading to pembrolizumab withdrawal
- TEAEs leading to study withdrawal
- TEAEs leading to death
- TEAEs by severity

- TEAEs by relationship to each IMP (related, not related) separately
- SAEs by relationship to each IMP separately

The number of events and the number and percentage of patients experiencing TEAEs will be presented by SOC and PT for the following TEAEs:

- Total TEAEs: If a patient experienced more than one TEAE, the patient will be counted once for each SOC and once for each PT. This summary will be repeated for serious TEAEs only.
- Total TEAEs by severity: If a patient experienced more than one TEAE, the patient will be counted once for each severity experienced during the study.
- TEAEs by relationship to each IMP: If a patient experienced more than one TEAE, the patient will be counted once for each SOC and once for each PT at the closest relationship to study drug. This summary will be repeated for serious TEAEs only.

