- TEAEs related to TG02 by severity. For this table, grade 1 and 2 events will be pooled. If a patient experienced more than one TEAE, the patient will be counted once for each severity experienced during the study. TEAEs related to GM-CSF, TEAEs related to TG02 and/or GM-CSF, TEAEs related to TG02 and/or GM-CSF only (i.e. events not related to pembrolizumab) and TEAEs related to pembrolizumab only will be summarised in an identical fashion.
- TEAEs leading to death.

In all of the tables described above, SOC and PT will be presented in decreasing frequency of the total number of patients with TEAEs.

All TEAEs will be listed with a separate listing for pre-treatment AEs. Separate listings of serious TEAEs and pre-treatment SAEs will also be presented.

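### For Part II, the planned related-by-severity tables do not in general give the number of patients with a grade 3 or higher event related to pembrolizumab or to any study drug

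*SAP*

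**What the plan says.** SAP 5.2 records causality separately for each product: "The relationship to each IMP (TG02, GM-CSF, pembrolizumab) is assessed as not related or related". One event can therefore be attributed to pembrolizumab and to TG02 or GM-CSF at the same time.

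The SAP then plans these SOC/PT tables, giving events and patients:

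- All TEAEs by grade, regardless of cause: "Total TEAEs by severity: If a patient experienced more than one TEAE, the patient will be counted once for each severity experienced during the study".
- A relationship table for each product, pembrolizumab included, with no split by grade, and the same again for serious events.
- Five related-by-severity tables. The first is described as "TEAEs related to TG02 by severity. For this table, grade 1 and 2 events will be pooled". The next two, for GM-CSF and for either vaccine component, follow the same layout. The last two are exclusive: "TEAEs related to TG02 and/or GM-CSF only (i.e. events not related to pembrolizumab) and TEAEs related to pembrolizumab only will be summarised".

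In the severity tables the counting rule is that "the patient will be counted once for each severity experienced during the study". Only grades 1 and 2 are pooled.

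The overview table has a row for IMP-related events, but it covers serious events only and is not split by grade.

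Protocol 11.6.1.1 lists "Related TEAEs by severity" and, as a separate item, TEAEs by relationship to each IMP. SAP 3.5, which records departures from the protocol's analysis, mentions only the efficacy analysis set.

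**The concern.** TG02 and GM-CSF each have a severity table that includes shared attributions. Pembrolizumab, the product that distinguishes Part II from Part I, has only an exclusive one. An event judged related to both pembrolizumab and TG02 appears in the TG02 tables but, by grade, in no pembrolizumab table. No severity table covers related events whatever the product, which is the natural reading of the protocol's item.

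The counting rule adds a second difficulty. A patient with one grade 3 and one grade 4 event appears in both rows, so the rows cannot safely be added to give patients with grade 3 or higher.

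At stake is a basic safety result. SAP 3.1 makes safety, in Part II that of the combination, one of two primary objectives. SAP 3.2 uses related toxicity of grade 3 or higher as the threshold for unacceptable TG02/GM-CSF reactions. A reader of the Part II report will want the patient rate at that grade for pembrolizumab and for the combination as a whole.

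**Working it through.** **Inputs**

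- Part II size, SAP 3.4: "approximately 4-6 patients in Part I and up to 10 patients in Part II if sponsor decision to initiate such".
- Attribution, table list and counting rule: SAP 5.2, as set out above.
- Neither document gives a figure to reproduce. The question is whether the planned tables determine the patient count.
- Reading adopted: the pembrolizumab-only table excludes events also related to TG02 or GM-CSF, in parallel with the item before it.

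**Step 1: events.** At any grade, related events fall into three separate classes: x, related to TG02 and/or GM-CSF but not pembrolizumab; y, pembrolizumab only; z, both. The tables show x + z, x, and y. Hence:

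- pembrolizumab-related events: y + z = y + (x + z) − x
- events related to any IMP: x + y + z = (x + z) + y

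Both identities held in 2000 of 2000 randomly generated datasets. Event counts are recoverable.

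**Step 2: patients, pembrolizumab.** Patients do not subtract in this way. Take two patients. Each has one grade 1 event related to pembrolizumab only and one grade 1 event related to TG02 and GM-CSF only. Assume no event is serious and each event term has its own SOC. Three grade 3 events are then placed in two ways:

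| Grade 3 event | Related to | Dataset 1 | Dataset 2 |
|---|---|---|---|
| a | pembrolizumab only | patient 1 | patient 1 |
| b | all three products | patient 1 | patient 2 |
| c | TG02 and GM-CSF, not pembrolizumab | patient 2 | patient 1 |

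The tables are the same for both datasets:

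| Table | Events / patients |
|---|---|
| All TEAEs, grade 3 | 3 / 2 |
| TG02, grade 3 | 2 / 2 |
| GM-CSF, grade 3 | 2 / 2 |
| TG02 and/or GM-CSF, grade 3 | 2 / 2 |
| The same, excluding pembrolizumab, grade 3 | 1 / 1 |
| Pembrolizumab only, grade 3 | 1 / 1 |
| Related to pembrolizumab, all grades | 4 / 2 |

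Events by Step 1: 1 + 2 − 1 = 2, correct in both. Patients with a pembrolizumab-related grade 3 event: **1** in dataset 1 (a and b both in patient 1), **2** in dataset 2.

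**Step 3: patients, any IMP.** Keep the grade 1 events and give both patients an unrelated grade 3 event. Patient 1 has a. Event c falls in patient 1 or in patient 2. The planned tables are again identical. Patients with a grade 3 event related to any IMP: **1** or **2**.

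**Step 4: counting rule alone.** Keep the grade 1 events and give both patients an unrelated grade 3 and an unrelated grade 4 event. Add one pembrolizumab-only grade 3 event and one pembrolizumab-only grade 4 event, either both in patient 1 or one in each patient. The pembrolizumab-only rows read 1/1 at grade 3 and 1/1 at grade 4 either way. Patients with a related grade 3 or higher event: **1** or **2**, on both measures.

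**Step 5: a wide case with ten patients.** Each patient has the two grade 1 events and an unrelated grade 3 event. Patients 1 to 5 have a pembrolizumab-only grade 3 event. Five shared grade 3 events fall either in patients 1 to 5 or in patients 6 to 10. At grade 3 both show: all TEAEs 20/10; TG02 and/or GM-CSF 5/5; the same excluding pembrolizumab 0/0; pembrolizumab only 5/5. Patients with a related grade 3 event: **5** or **10** of 10 (50% or 100%), on both measures. This is built to show the spread and is not a forecast.

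**The case against.** Much of the information is planned in some form. Event counts follow from Step 1. The relationship tables count shared attributions as pembrolizumab-related, for all and for serious TEAEs, with patient numbers: "TEAEs by relationship to each IMP: If a patient experienced more than one TEAE, the patient will be counted once for each SOC and once" per PT. What they lack is grade. A reader might infer that the plan understates pembrolizumab toxicity, but the exclusive table is labelled as such and the inclusive patient count, ungraded, is planned elsewhere.

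A reader might also infer that the count can never be obtained, or that data are lost. Neither follows. The tables can fix the number when the relevant cells are zero, or when they show that every grade 3 or higher event is related to pembrolizumab and all fall in one grade. All TEAEs are listed, and with at most 10 patients a hand count is possible if the listing shows grade and relationship. The shells are a separate document, so this cannot be confirmed.

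The protocol does not define related as related to any IMP, and the SAP's five tables could be defended as a product-by-product version of its item. Counting once per severity is stated openly and is not an error in itself. The analysis is descriptive (SAP 6.4.1), and no stated decision rule uses the missing rate.

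All of this stands and limits the size of the point. None of it provides a planned patient count at grade 3 or higher for either measure.

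**Conclusion.** The gap is real but modest: one of reporting, not of data. No planned table gives the number of Part II patients with a grade 3 or higher event related to pembrolizumab or to any IMP, and in general that number cannot be worked out from the planned tables. In the small examples the ambiguity is one patient; with ten patients each one is worth 10 percentage points (1/10). The documents do not say how often attribution will be shared, so the ambiguity that will actually arise cannot be estimated.

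The pembrolizumab part rests on reading the last table as exclusive. If it was meant to hold all pembrolizumab-related events, Step 2 would be resolved. Steps 3 and 4 would remain, and with them the any-IMP gap and the overlap between grades.

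The difference from the protocol's list should be reconciled whichever reading of related was intended, since SAP 3.5 is silent. The point is worth correcting before database lock because combination safety is a primary objective and the correction is cheap.

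**What to change.** In SAP 5.2, add two related-by-severity tables:

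1. TEAEs related to pembrolizumab, with or without TG02/GM-CSF.
2. TEAEs related to any IMP. This also provides the table in Protocol 11.6.1.1 on its natural reading.

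Give each a row for the number and percentage of patients with at least one grade 3 or higher event, each patient counted once. The existing tables and their once-per-severity rows can stay. The new rows would show directly the 1 or 2 patients of Steps 2 to 4, and the 5 or 10 of Step 5.

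The cost is two extra tables from data already collected. SAP 1 already provides for a review and revision before database lock.

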5.3 Clinical Laboratory Evaluation

The clinical laboratory tests to be performed are presented in Table 9-1: Clinical laboratory parameters of the protocol. For each laboratory parameter, the baseline value will be defined as the last scheduled or unscheduled value collected prior to the first dose of IMP. If the times of assessments have not been recorded, assessments carried out on the day of first IMP administration are considered to have taken place before IMP administration. For post baseline, only data from scheduled visits will be included in the summary tables. Percent change from baseline will be calculated as $100 * (\text{observed value} - \text{baseline value}) / \text{baseline value}$.

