6.1. Endpoints

Primary endpoints:

- Safety:
 - Adverse events
 - Laboratory assessments
 - Vital signs
- Systemic immune responses assessed by:
 - TG02-specific DTH response
 - Presence of TG02 specific T-cells in peripheral blood
 - Change in intra-tumoural lymphocytes

Secondary endpoints:

- Immune suppression factors in tumour specimens
- Pathological responses and markers of apoptosis in tumour specimens
- Change in standard uptake values (SUV) assessed by FDG PET-CT
- Change in CEA

Exploratory Endpoints:

[figure not shown]
- Change in circulating tumour cells and/or circulating tumour DNA
- Functionality of RAS mutation specific T cells in tumour tissue and peripheral blood

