The reporting of laboratory/vital signs abnormalities as both laboratory findings and adverse events should be avoided. They should not be reported as AEs unless any criterion of clinical significance and/or a SAE is fulfilled, the laboratory/vital signs abnormalities cause study drug dose adjustment, lead to patient discontinuation of their trial treatment, or the investigator insists that the abnormality is reported as an AE. If an abnormal laboratory

value/vital sign is associated with clinical signs and symptoms, the sign/symptom should be reported as an AE and the associated laboratory result/vital sign should be considered additional information that must be collected on the relevant CRF.

All patients who have new or worsening NCI-CTC grade 3 or 4 laboratory values at the time of withdrawal must have further tests performed and the results recorded on the appropriate CRF, until the laboratory values have returned to NCI-CTC grade 1 or 2, unless these values are not likely to improve because of the underlying disease. In these cases, the investigators must record their opinions on the CRFs and in the patients' medical records. For an AE to be a suspected drug-related event there should be at least a reasonable possibility of a causal relationship between the trial medicinal product and the AE (see [Appendix II](#) for guidelines on interpretation of causality).

It is important to distinguish between serious and severe AEs. Severity is a measure of intensity whereas seriousness is defined by the criteria in [section 9.2](#). An AE of severe intensity need not necessarily be considered serious. For example, nausea that persists for several hours may be considered severe nausea, but is not an SAE. On the other hand, a stroke that results in only a limited degree of disability may be considered a mild stroke, but would be an SAE.

Lack of efficacy

When there is deterioration in the condition for which the medicine is being used there may be uncertainty as to whether this is lack of efficacy or an AE. In such cases, unless Targovax or the reporting physician considers that the medicine contributed to the deterioration or local regulations state to the contrary, **the deterioration should be considered to be a lack of efficacy and not an AE.**

Handling unresolved SAEs/AEs at completion/withdrawal

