9.2.2. Safety Laboratory Variables

Safety serum chemistry and haematology parameters will be analysed at hospitals local laboratory.

Blood samples for the determination of serum chemistry and haematology will be drawn at pre-specified time-points, see Schedule of visits ([Table 6-1](#)) Additional haematology and chemistry are under the investigator's judgement.

The following laboratory tests will be performed:

Table 9-1: Clinical laboratory parameters

Chemistry	Haematology
Total Alkaline Phosphatase (total ALP)	RBC count
ALT (SGPT)	Hb
AST (SGOT)	Haematocrit
Lactate Dehydrogenase (LDH)	PLT count
Gamma-GT	WBC count
Total Protein	WBC diff.
Albumin	Neutrophils
Bilirubin	Lymphocytes
Creatinine	Monocytes
Sodium	Eosinophils

Chemistry	Haematology
Potassium	Basophils
Magnesium	
Calcium	
Phosphate	
Chloride	
Urea	
Oestradiol (females at screening only)	

Reference ranges from each laboratory will be provided to the Sponsor. If during the study, ranges should be changed, investigators are requested to provide updated laboratory normal values.

Laboratory values with CTCAE grade 3 or higher and/or considered clinically significant by the treating physician have to be reported as an AE during the treatment period. At the follow-up visit only changes in laboratory values judged to be related to the study drug will be reported.

Volume to be drawn from each patient

The total volume of blood that will be drawn from each patient in this trial will vary depending on how long the patient stays on study. [Table 9-2](#) indicates the range for patients completing the whole study period.

Table 9-2: Volume of blood to be drawn from each subject

Assessment		Sample volume (ml)	No. of samples	Total volume (ml)
PBMC		50 ml	2-3	100-150 ml
Biomarkers (CEA)/ other immune subsets		7 ml	2-3	14-21 ml
Safety	Clinical chemistry	7 ml	5-6	35-42 ml
	Haematology	7 ml	5-6	35-42 ml
CTCs		6 ml	2-3	12-18 ml
Total		67 ml		196-273 ml

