5.3.1 Haematology

Summary statistics of haematology observed values, change from baseline and percent change from baseline will be presented for all patients by parameter and visit.

In addition, a shift table showing the movement of patients with respect to CTC grade (according to NCI CTCAE v4.03) from baseline to each study visit will be presented by parameter. Patients will only be included in the missing category if they attended the respective post baseline visit but have no data available for that

parameter. Patients withdrawing prior to baseline will not be included in the missing category.

Individual patient haematology values will be plotted, with separate pages for each treatment group and parameter. Additionally, box plots will be produced to summarize values over time, with separate pages for each treatment group and parameter.

All haematology values will be listed showing reference ranges and flagging all abnormal findings and their clinical significance. Out of reference ranges will be flagged as high (H) or low (L).

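### SAP 5.3 builds the post-baseline laboratory tables, including the CTC-grade shift, from scheduled visits only with no worst-grade table, and a laboratory count planned in the protocol is missing without being declared

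*SAP*

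**What the plan says.** Protocol 6.1 lists "Laboratory assessments" among the primary safety endpoints. Protocol 9.2.2 foresees tests outside the schedule: "Additional haematology and chemistry are under the investigator's judgement". Under protocol 9.2.1.2, patients with new or worsening grade 3 or 4 laboratory values at withdrawal "must have further tests performed and the results recorded on the appropriate CRF".

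For the analysis, SAP 5.3 admits off-schedule values before treatment ("the baseline value will be defined as the last scheduled or unscheduled value collected prior to the first dose of IMP") but not afterwards ("For post baseline, only data from scheduled visits will be included in the summary tables"). SAP 5.3.1 then plans "a shift table showing the movement of patients with respect to CTC grade (according to NCI CTCAE v4.03) from baseline to each study visit". SAP 5.3.2 treats clinical chemistry in the same way. The SAP text describes no table of worst post-baseline grade.

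Protocol 11.6.1.1 also commits to a count: "number of patients with abnormal and/or clinical significant values will be presented by time point". SAP 5.3 has no matching table; clinical significance appears there only as a flag in the listings. SAP 3.5, which records departures from the protocol's analysis, mentions only the efficacy analysis set.

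**The concern.** Unscheduled tests are usually ordered because something is suspected, so they are plausibly more likely than routine draws to be abnormal. That is an inference; the documents give no data on it. A rule that keeps them out of every post-baseline laboratory table would then make those tables look cleaner than the data.

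Scheduled-only data are sensible for by-visit means, where an extra value has no natural visit to belong to. A grade shift serves another purpose: it should show how bad each parameter became in each patient. Applying the by-visit rule to it, with no worst-grade table beside it, leaves that question without a tabulated answer. In groups of 4 to 10 patients, one patient visibly changes a percentage.

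**Working it through.** The plan states no power, alpha or rate to reproduce; the study is descriptive. The check is of which values reach which output.

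**Schedule.** Protocol 6.4.2 and Table 6-1 place haematology and biochemistry on Days 1, 15, 36, 50 and, if surgery is after week 10, Day 64. The gaps are 15 − 1 = 14, 36 − 15 = 21, 50 − 36 = 14 and 64 − 50 = 14 days. In Part II pembrolizumab starts on Day 22, inside the 21-day gap. Table 6-1 marks no draws in the Day 51-63 and Day 65-92 columns. End-of-study results may be taken from the medical record.

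**Where an off-schedule post-baseline value appears**

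| Value | Laboratory tables | TEAE tables | Listings |
|---|---|---|---|
| Grade 3 or higher, treatment period | No | Yes (protocol 9.2.2) | Yes |
| Grade 1-2, judged clinically significant, treatment period | No | Yes (protocol 9.2.2) | Yes |
| Grade 1-2, not judged clinically significant | No | Generally no | Yes |
| Found at follow-up | No | Only if judged related to study drug | Yes |

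An abnormality that lasts to the next scheduled draw is tabulated there, though possibly below its peak grade.

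**How easily a transient abnormality falls between draws (illustration).** Assume onset is uniform over the schedule and the value is abnormal for exactly L days. The share lying wholly between draws is Σ max(0, gap − L) / Σ gap.

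- Draws to Day 50 (Σ gap = 49). L = 3: (11 + 18 + 11)/49 = 82%. L = 7: (7 + 14 + 7)/49 = 57%. L = 10: (4 + 11 + 4)/49 = 39%. L = 14: 7/49 = 14%. L = 21: 0%.
- Draws to Day 64 (Σ gap = 63). The same lengths give 81%, 56%, 37%, 11% and 0%.

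These shares describe the schedule, not the number of values lost. A value is in the database to be excluded only if someone ordered the test.

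**Weight of one patient.** 1/10 = 10 percentage points; 1/6 = 16.7; 1/4 = 25.

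**The protocol's count.** Protocol 11.6.1.1 asks for it by time point. The by-visit grade shift covers part of it, because graded abnormalities can be read off at each visit. The clinical-significance part has no table in the SAP text.

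**The case against.** A reader might infer that toxicity found on unscheduled tests disappears from the report. The documents do not support that. Protocol 9.2.2 requires values of grade 3 or higher, or judged clinically significant, to be reported as adverse events in the treatment period, whether or not the test was scheduled. SAP 5.2 tabulates those events by system organ class, preferred term and severity, at the maximum grade of each event. Adverse events are themselves a primary safety endpoint. All laboratory values are listed with abnormal findings flagged. Individual patient values are plotted, and the scheduled-only sentence does not restrict the plots. A grade 3 liver value on an unscheduled Day 29 test would be absent from the laboratory shift table but should count as a TEAE. This objection stands and sets the limit of the point.

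The adverse event route is not complete. Protocol 9.2.1.2 discourages reporting a laboratory abnormality both ways; its exceptions include clinical significance but do not name grade 3, which sits uneasily with 9.2.2. A grade 3 TEAE beside a shift table showing none would also leave two safety tables in apparent conflict.

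Three further limits also stand. Using the last pre-dose value as baseline and scheduled visits for by-visit summaries is a usual convention, so the different treatment of baseline is not itself an inconsistency. The table shells are a separate document (SAP 1) that was not available; a worst-grade table there cannot be ruled out, but if it used unscheduled values it would contradict SAP 5.3 as written. Finally, one might extend the point to ECOG, which follows the same rule in SAP 5.6. That case is weak: ECOG is not among the primary endpoints in protocol 6.1, it is assessed at every scheduled treatment visit, and the protocol makes no provision for extra assessments.

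**Conclusion.** The point holds for the laboratory tables only. As written, SAP 5.3 leaves out of them any post-baseline abnormality seen only off schedule, and any peak grade between draws. The real loss is mainly grade 1-2 values found off schedule and not judged clinically significant, plus possible disagreement between the laboratory shift and the adverse event tables. This assumes that investigators follow the reporting rule in protocol 9.2.2.

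The size cannot be estimated, because the documents give no rate of unscheduled testing. The figures of 10, 16.7 and 25 percentage points are the weight of one hypothetical patient, not an expected bias.

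The missing count from protocol 11.6.1.1 is a separate, smaller discrepancy. It holds whatever view is taken of unscheduled values: the SAP text describes no such table and SAP 3.5 does not declare a change. The protocol promised the count by time point only, so a pooled patient-level count or a worst-grade table would be a new analysis.

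**What to change.** Keep the by-visit laboratory summaries on scheduled values. Then make two changes.

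1. Add to SAP 5.3 a shift table from baseline to worst post-baseline CTC grade for each haematology and chemistry parameter, with high and low directions shown separately, using all scheduled and unscheduled values. State whether values after surgery are included, since the end-of-study draw falls in postoperative recovery.
2. Reinstate the by-time-point count of patients with abnormal or clinically significant values from protocol 11.6.1.1, or declare its removal in SAP 3.5.

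The cost is a little extra programming on data already planned for collection and listing; no patient procedure changes. The stated laboratory toxicity may look slightly less favourable.
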